A Pilot Dose-Response Biomarker Study of Brexpiprazole Treatment in PTSD
(Terminated)

NCT02934932

Document Date: February 3, 2017

1. Title: A Pilot Dose-Response Biomarker Study of Brexpiprazole Treatment in PTSD

2. Purpose of the Study: To determine if brexpiprazole treatment will be associated with a dose-dependent reduction in resting pupil diameter as a reflection of locus coeruleus (LC) norepinephrine (NE) neuron target engagement in a group of subjects with PTSD. To determine if brexpiprazole therapy will also be associated with a dose-dependent decrease in the clinician administered PTSD scale (CAPS-5) scores. To determine if the pre-post treatment change in resting pupil diameter will be statistically significantly correlated with the pre-post change in CAPS-5 score.

3. Primary Objectives:

Specific Aim 1: Evaluate the effects of two doses of brexpiprazole on locus coeruleus (LC) norepinephrine (NE) neuron activity.

Specific Aim 2: Determine the effect of brexpiprazole therapy on PTSD symptom severity.

Specific Aim 3: 1) Evaluate whether depression severity improves with treatment and assess how this relates to PTSD response; 2) Specifically evaluate the degree to which treatment improves nightmares; 3) Evaluate the effects of treatment on sleep disturbance.

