Inclusion/Exclusion Participants will be 18-65 years of age. All subjects will be evaluated by physical examination, ECG, standard blood chemistry, hematologic labs, toxicology testing, Compliance Panel and urinalysis at baseline and end of study. Results of these studies must demonstrate a lack of clinically significant abnormalities prior to enrollment. If results are outside of the normal reference range the study physician will be consulted to assess if clinically significant. Subjects will need to satisfy DSM-5 criteria for PTSD and receive a CAPS-5 score of 33 or greater on testing for study enrollment. Subjects will need to be free of psychotropic medications or treatments that could impact results of this study as deemed by the PI for at least 1 week. If the subject's primary psychiatrist or treating primary care physician are providing the subject with psychotropic medications they will be notified and a discussion about tapering current psychotropic medications prior to study enrollment will occur.

Exclusion Criteria.

The exclusion criteria is in accordance with the package insert for brexpiprazole and can be located at https://www.accessdata.fda.gov/drugsatfda_docs/label/2015/205422s0001bl.pdf

- 1) Subjects will be excluded if they have significant medical or neurologic conditions (other than mild to moderate TBI), specifically seizures, or movement disorders,
- 2) have substance abuse within 12 months of study enrollment, substance dependence within past three months, per DSM-5 criteria (excluding caffeine and nicotine). The absence of substance use will be determined by self-report and confirmed by the results of urine toxicology at screening.
- 3) Women who are pregnant, breast-feeding, or planning to become pregnant while enrolled in this study will also be excluded.

- 4) Subjects with a history of severe drug allergy or hypersensitivity, or known hypersensitivity to the Brexpiprazole or its ingredients.
- 5) The subject has a history of tardive dyskinesia.
- 6) The subject has clinically significant extrapyramidal symptoms (EPS) including akathisia.
- 7) The subject has epilepsy or a history of seizures, except for a single seizure episode (e.g., childhood febrile seizure, post traumatic, or alcohol withdrawal).
- 8) The subject has chronic, uncontrolled, or unstable clinically relevant medical conditions Including:
 - Uncontrolled hypertension defined as blood pressure greater than 180/90

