 - Hypotension defined as a blood pressure less than 90/60
 - Moderate to severe hepatic impairment (Child-Pugh score ≥ 7)
 - Moderate, Severe or End-Stage Renal Impairment (CrCL < 60 ml/min)
 - Known CYP2D6 Poor Metabolizers
 - Heart failure NYHA Class III or IV
 - Diabetes mellitus or HbA1c greater than 5.7% (which defines pre-diabetes)
 - Hypertriglyceridemia defined as triglycerides greater than 200mg/dL
 - Low white blood cell count (below lower range of normal)
 - History of leukopenia or neutropenia
 - Arrhythmia with heart rate greater than 100bpm
 - Myocardial infarction in the past 6 months
 - Cerebrovascular accident in the past 6 months
 - Recurrent syncope
 - Seizure disorder
 - Currently receiving treatment for malignancy
 - QTc interval of greater than 450ms on electrocardiogram
- 9) The subject has a neurodegenerative disorder (Alzheimer disease, Parkinson's disease, multiple sclerosis, Huntington disease, etc.).

5.2 Study Components: There are 3 treatments (placebo, 2mg, 4mg), each for six weeks (± 3 days), separated by a 1 week (± 3 days) wash-out period. Each subject will be randomly assigned to three of the treatments. Subjects will undergo three treatments and receive 42 doses of study drug during each of the three treatment phases. Each treatment phase lasts for 6 weeks (± 3 days). For each subject, they will receive a total of 126 doses of study drug. For the brexpiprazole treatment arms, we will begin with 1mg PO q Day on Days 1 through 4 and titrate to 2mg q Day on Days 5 -7 (i.e., the 2mg brexpiprazole group will continue on 2mg daily for the remainder of the 6 weeks), and then to 4mg/day on Day 8 (i.e., this will be for the 4mg brexpiprazole group who will continue on this dose for the remainder of the 6 weeks). Irrespective of the treatment group, including placebo, subjects will be assigned three medication bottles indicated to be taken during days 1-4, days 5-7, and days 8 and up to ensure blinding during the three treatment arms. Otsuka will be providing the study medication as a bulk supply and each medication dose and placebo will look identical to each other. The study drug will be stored in a double locked medicine cabinet in the Duke Sleep Lab (Duke Clinic, 5th floor Red Zone). [name] will be creating a randomization algorithm that will be given to an unblinded study staff member to use during randomizations. The unblinded study member will prepare the study drug to be dispensed to the subjects.

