Subjects will be screened and will undergo pupil measures with rating scales on Day 1. Subject must be free of all psychotropic medications for one week before Day 1 assessment, except that prior fluoxetine treatment will require 4 weeks of abstinence, and MAOIs will require 2 weeks of abstinence. They will be randomized to study drug and issued six weeks of study medication on Day 1 to take home. A phone call will then occur for safety assessment and medication adherence at every week. They will present back to the study site on Day 42 and undergo pupil measures with rating scales. They will then undergo a one week washout period. On Day 49 they will then be given another study drug to take home with rating scales and pupil measures obtained that day. A phone call will then occur for safety assessment and medication adherence at every week. They will present back to the study site on Day 91 and undergo pupil measures with rating scales. They will then undergo a one week washout period. On Day 98 they will then be given another study drug to take home with rating scales and pupil measures obtained that day. A phone call will then occur for safety assessment and medication adherence at every week. They will present back to the study site on Day 140 and undergo pupil measures with rating scales. No more study medication will be provide on Day 140 and a final visit will be scheduled for on Day 147, one week later, for and end of study interview with labs and physical exam. At each visit, other than the final visit, subjects will complete the CAPS-5, LEC-5, MADRS, Insomnia Severity Index, Columbia Suicide Severity Rating Scale, and Clinician Assessment for Adverse Effects.

5.3 Pupilometry Procedure. We will employ Tobii Tracker Eyeglasses 2 (Stockholm, Sweden) fully mobile Eye-tracking Glasses, a non-invasive system designed to be used like a common pair of glasses (weight 75 g) in a wide range of environments, both indoors and outdoors. Pupil diameter will be recorded continuously from the each eye at a sampling rate of 50 - 100 Hz via glasses on the subject's face in a darkened room.

Primary Hypothesis: Brexpiprazole treatment will be associated with dose-dependent reduction in resting pupil diameter as a reflection of LC NE neuron target engagement in a group of subjects with PTSD.

Secondary Hypothesis: Brexpiprazole therapy will be associated with a dose-dependent decrease in CAPS-5 scores

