Tertiary Hypothesis: The pre-post treatment change in resting pupil diameter will be statistically significantly correlated with the pre-post change in CAPS-5 score.

Version: 2/3/2017

5.4 Sample Size Justification and Power Analysis: We chose an effect size of 0.3 as 6/8 prior trials of the effects of atypical antipsychotic medications on PTSD using the CAPS-5 had effect sizes larger than this and we felt that an effect of this size or larger would be clinically relevant (Liu et al., 2014). The effect-size calculation was based on the Cohen's D measure of effect size (mean difference divided by overall standard deviation). We are enrolling a sufficient number of subjects in a 3-way cross-over design study so that we could both detect this effect AND be able to detect the pupil size effect with at least 80% power. In order to address the issue of powering for 2 outcome measures we will employ Bonferoni correction to be conservative and to achieve 80% power to detect BOTH the CAPS-5 and pupil size effects at the $\alpha=0.025$ level of significance (Bonferoni correction for 2 tests dictates that we divide the $\alpha=0.05$ level by 2). We calculated that with 36 subjects we could achieve greater than 80% power to detect effects with BOTH the CAPS-5 and pupil measure at the $\alpha=0.025$ level in a one-tailed test of significance (we are only interested in whether brexpiprazole is associated with lower CAPS-5 scores and pupil diameters than placebo and will only test this hypothesis and will not test whether placebo has a greater therapeutic effect than brexpiprazole). This calculation assumed an effect size of 0.3 for both the CAPS-5 score and for the pupil measure. It should be noted that the assumption of an effect size of 0.3 for the pupil measure is highly conservative. We can estimate the effect size for the between group differences in pupil size based on our pilot work where we compared pupil size in a group of patients with depression and anxiety ($n=5$) and healthy controls ($n=5$) using the pupillometric measure to be used in the proposed study. We hypothesize that the difference in locus coeruleus norepinephrine activity (which determines pupil size in this test) in PTSD subjects will be comparable to or larger than the differences in locus coeruleus activity in patients with depression associated anxiety. The basis for this hypothesis is that the patients we studied likely have less severe arousal-system dysfunction than PTSD patients who manifest symptoms of hypervigilance which is likely to activate locus coeruleus to a comparable or greater degree and be reflected in pupillometry. The effect size for the difference in resting pupil diameter in our anxious/depressed patients and healthy controls is 2.98 based on Cohen's D. However, it is appreciated that this is derived from a very small sample of subjects who are not the identical patient population that we will be studying so we assumed that it was most conservative to assume a lower effect size than 2.98. As a result, we assume an effect size of 0.3 which is likely quite conservative for power with respect to the pupil size measure. Thus, we propose to enroll 36 subjects in our study and believe that this is conservative for having more than 80% to detect effect sizes of 0.3 for both the CAPS-5 and pupil measures with an $\alpha=0.025$, which is adjusted from 0.05 for detecting effects on 2 primary outcomes at the 0.05 level, in one-tailed tests of significance.

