- Stuffy or runny nose, upper respiratory tract infection like common cold or bronchitis
- Abnormal liver function test (a blood measurement for the state of the liver), blood creatine phosphokinase increase (a blood test to diagnose for example muscular damage).
- Increased appetite, weight gain
- Elevated blood sugar or development of diabetes mellitus
- Increase in blood cholesterol levels
- Back pain
- Restlessness, seizure, dizziness, movement disturbances, headache, sedation, drowsiness or fatigue trembling.
- Seizures
- Agitation, anxiety

For some patients, who have not responded to treatment with brexpiprazole, have experienced a re-occurrence of disease symptoms have been reported such as symptoms associated with schizophrenia, psychotic disorder, depression or suicidal thoughts.

Although a placebo has no known risk, it may be associated with higher rates of suicidal thoughts. Risks associated with drawing blood from the arm may include momentary discomfort and/or bruising. Infection, excess bleeding, clotting, or fainting are also possible, although unlikely. There is also a risk that psychiatric symptoms may worsen during the study, particularly during the period where individuals may be tapering off of medications.

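### Does the tertiary pupil and CAPS-5 correlation need a stated model because the crossover yields three change pairs per subject?

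*Combined protocol and SAP*

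**What the plan says.** The combined protocol and SAP gives the tertiary test twice, both times as an aim and not as an analysis. Section 2 (Purpose of the Study) has "To determine if the pre-post treatment change in resting pupil diameter will be statistically significantly correlated with the pre-post change in CAPS-5 score"; the Tertiary Hypothesis has "The pre-post treatment change in resting pupil diameter will be statistically significantly correlated with the pre-post change in CAPS-5 score". Neither place gives a coefficient, model, unit of analysis, alpha level, sidedness or definition of the starting measurement.

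Section 5.2 sets the data structure: "Subjects will undergo three treatments and receive 42 doses of study drug during each of the three treatment phases". Pupil and rating scales are taken at the start and end of each period (Days 1 and 42, 49 and 91, 98 and 140). For period 2, for instance, "On Day 49 they will then be given another study drug to take home with rating scales and pupil measures obtained that day".

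Three statements bear on whether Day 1 could be unusual. Entry requires subjects to "receive a CAPS-5 score of 33 or greater on testing for study enrollment". For those on medication, "a discussion about tapering current psychotropic medications prior to study enrollment will occur", and section 6.3 warns that "psychiatric symptoms may worsen during the study, particularly during the period where individuals may be tapering off of medications". Against this, section 5.2 states that "Subject must be free of all psychotropic medications for one week before Day 1 assessment".

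Section 5.4 divides alpha between two outcomes, CAPS-5 and pupil size, and leaves the correlation out. The text then moves to consent. There is no analysis section for any outcome.

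**The concern.** A plain correlation assumes independent pairs. Here three pairs come from each person, and period or dose could move both measures at once. At least three readings fit the sentence: pool all 108 pairs, use one treatment only (36 pairs), or average within subject (36 pairs).

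Pooling without adjustment can reject too often in two ways. First, if both measures run high at Day 1 and then settle, the period 1 changes in both are shifted together. The entry threshold and the taper make this plausible for CAPS-5. Second, if people differ in their average change, the three pairs from one person are not independent.

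At stake is one of the three stated purposes, and the only stated test that ties the pupil biomarker to PTSD symptoms.

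**Working it through.** **Inputs.** From the document: 36 subjects (section 5.4), three periods with paired measures (section 5.2), so at most 36 × 3 = 108 pairs if nobody drops out. There is no stated figure to reproduce for this test; the power above 80% in section 5.4 concerns the two mean effects. Everything else is assumed: a two-sided 5% test, unit variance at each visit, equal correlation ρ among the six visits, and six treatment orders with 6 subjects each.

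**1. The unit matters.** By Fisher's z, the critical r is tanh(1.96/√(N−3)), and the r detected with 80% power is tanh((1.96+0.842)/√(N−3)).
- N = 36 (√33 = 5.745): 0.33 and 0.45.
- N = 108 (√105 = 10.247): 0.19 and 0.27.

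**2. Three pairs per person do not by themselves inflate the error.** With each period's own baseline, the covariance of two changes in one person is ρ − ρ − ρ + ρ = 0, so stable differences in level cancel. Simulated pooled error is 5.2%.

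If subjects also differ in average change, with share ICC of the change variance in each measure and no link between the two, the design effect is 1 + 2·ICC².
- ICC 0.3: 1.18, error 2[1 − Φ(1.96/√1.18)] = 7.1%.
- ICC 0.5: 1.50, error 2[1 − Φ(1.96/√1.50)] = 11.0%.
- Simulation at shares of 13%, 29% and 50%: 5.3%, 7.3% and 11.1%.
- ICC 0.7 would give 16.4%, with most of the change variance lying between people.

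If all three changes were taken from Day 1, the correlation between them would be (1−ρ)/[2(1−ρ)] = 0.5, again about 11% (simulated 11.2%).

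**3. Shift s at Day 1 in both measures, pooled.** Period mean changes are (−s, 0, 0), with variance (1/3)(2/3)s² = (2/9)s². The spurious correlation is (2/9)s² / [2(1−ρ) + (2/9)s²]. At s = 0.5 the numerator is 0.0556:

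| ρ | spurious r | error, Fisher z | error, simulated |
|---|---|---|---|
| 0.5 | 0.0556/1.0556 = 0.053 | 8.4% | 8.5% |
| 0.7 | 0.0556/0.6556 = 0.085 | 14.0% | 14.2% |
| 0.8 | 0.0556/0.4556 = 0.122 | 24.1% | 24.3% |

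At s = 0.3 the simulated errors are 5.4%, 6.2% and 7.6%. A 0.5 SD CAPS-5 shift with a 0.2 SD pupil shift gives 6.9% (ρ 0.7) and 7.9% (ρ 0.8). A CAPS-5 shift alone gives 5.0% and 5.1%.

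**4. Other readings under the 0.5 SD double shift.** One treatment only gives 6.0%, 7.9% and 10.9% at ρ 0.5, 0.7 and 0.8. Subject means give 4.8% to 5.0%: every completer has one period 1 and all three treatments, so both effects add the same constant to each subject's mean and drop out.

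**5. Real drug effects.** With changes scaled to SD 1, dose effects of 0.3 and 0.6 SD on both measures give 8.3% pooled. Adding a 0.5 SD period 1 shift gives 21.2% with ICC 0.3, and 22.2% with a common Day 1 baseline. Part of this is the drug moving both measures, which the hypothesis can fairly be read as seeking.

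**6. What a prescribed model would cost.** Power at a within-person correlation of 0.3 (ρ 0.7, dose effects 0.15 and 0.30 SD):

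| Analysis | no subject differences | subject SD of average change 0.5 |
|---|---|---|
| Pooled | 93% | 65% |
| One treatment | 44% | 24% |
| Subject means | 44% | 12% |
| Period + treatment | 89% | 57% |
| Period + treatment + fixed subject | 72% | 72% |

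The last row keeps the error near 5% in all no-link cases run. But if the link lies only between people (subject SD 0.77, between-subject correlation 0.8), subject means reject 98% of the time and the fixed-subject model about 5%.

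**The case for a change.** The best case for a change is that a hypothesis predicting significance should name its test. The critical r falls from 0.33 to 0.19 according to the unit chosen, so the same data could pass or fail on a choice made after unblinding. A model with period, treatment and subject terms holds its error near 5%, needs no new data, and costs a paragraph.

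Part of this stands. The unit, the starting measurement (Day 1 or each period's own), the sidedness and the within-person or between-person question are all open, and whoever analyses the data must settle them.

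The rest is weaker. The 44% to 93% power range scores every method against a within-person link only, and the document never says the question is within-person. Asking whether people whose pupils shrink more also improve more is an equally natural reading, and fixed subject terms cannot see that link. Asking only for subject effects also leaves fixed or random open. A random intercept with period and treatment terms gave 87% power against 72% for fixed terms when subjects did not differ in average change, 71% for both at subject SD 0.5, and an error of 5% to 6% in the no-link cases. The proposed model is therefore one defensible choice among several.

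**Conclusion.** The gap exists, but it is missing detail of a kind that analysts fill sensibly. The document states a hypothesis and commits to no faulty test. A statistician with crossover data would not ordinarily treat 108 repeated pairs as independent, and subject means hold 5% in every no-link case run. The lack of a model is also common to all outcomes and not particular to this one.

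If someone did pool carelessly, the error would be about 5% to 11% under moderate assumptions: a 0.3 SD double shift, a CAPS-5 shift with a smaller pupil shift, or up to half of the change variance lying between subjects. Going from 14% to 24% requires a 0.5 SD Day 1 shift in both measures with ρ of 0.7 to 0.8. No section describes such a pupil shift. The medication-free week works against a Day 1 excess, and so may a separate screening visit: section 6 pays for 8 visits while section 5.2 dates 7.

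Prescribing one model would trade power and the between-person question for error control that simpler choices already give. For a tertiary test in a pilot, outside the alpha split, no change follows. All rates rest on assumed correlations, shifts and subject variances, since the document gives none.

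### Section 5.4 claims more than 80% power to detect both CAPS-5 and pupil effects, but the Bonferroni split it relies on does not give joint power and no joint calculation is shown

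*Combined protocol and SAP*

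**What the plan says.** Section 5.4 (Sample Size Justification and Power Analysis) names one step for handling two outcomes: "In order to address the issue of powering for 2 outcome measures we will employ Bonferoni correction to be conservative". The same sentence gives the purpose of that step as "to achieve 80% power to detect BOTH the CAPS-5 and pupil size effects", with 0.05 divided by 2 to give 0.025.

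The result is then stated: "We calculated that with 36 subjects we could achieve greater than 80% power to detect effects with BOTH the CAPS-5 and pupil measure", each test being one-tailed at 0.025. On the inputs, "This calculation assumed an effect size of 0.3 for both the CAPS-5 score and for the pupil measure", where the effect size is Cohen's d on the overall standard deviation. The closing sentence of the section repeats that power exceeds 80% for the two outcomes.

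Section 5.4 does not name the contrast that was powered. It gives no within-subject correlation, no correlation between the two outcomes, no per-test power beyond exceeding 80%, and no joint calculation. The tertiary hypothesis expects the changes in pupil diameter and CAPS-5 to be correlated, but attaches no figure.

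**The concern.** A Bonferroni split bounds the chance of at least one false positive across two tests. The chance that both tests are positive when both effects are real is a different quantity. It depends on the power of each test and on the correlation between the two test statistics. Section 5.4 treats the first as if it delivered the second.

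At stake is the figure offered to justify N = 36. A reader who takes it at face value will put the risk of missing at least one of two real effects below 20%. If the underlying figure is 80% per test, that risk is 36% at correlation 0 and still 25% at correlation 0.9.

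**Working it through.** **Inputs from the protocol.** N = 36; three treatments per subject in a crossover (Sections 5.1 and 5.2); d = 0.3 on the overall SD for each outcome; one-sided alpha 0.025 per test (Section 5.4).

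**Inputs assumed because none is stated.** Within-subject correlation ρ, taken from 0 to 0.9; correlation r between the two test statistics, taken from 0 to 0.9. For paired tests on the same subjects, r is approximately the correlation between the within-subject treatment differences in the two outcomes.

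**Step 1: the plan's own figure.** For one dose against placebo, the standardised paired difference is 0.3/√(2(1−ρ)), tested by a noncentral t with 35 df. For the two doses pooled against placebo, it is 0.3/√(1.5(1−ρ)) with 70 df.

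| ρ | One dose vs placebo | Pooled doses vs placebo |
|---|---|---|
| 0 | 23.5% | 30.5% |
| 0.5 | 41.7% | 53.6% |
| 0.7 | 61.8% | 75.4% |
| 0.8 | 79.0% | 90.0% |
| 0.85 | 89.2% | 96.3% |

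Per-test power reaches 80% at ρ of about 0.80 (one dose) or 0.73 (pooled). Since ρ is not stated, the figure of more than 80% can be neither reproduced nor refuted. Treating 0.3 as Cohen's f in a repeated-measures F test gives 95.8% at ρ = 0.5, but Section 5.4 says Cohen's d.

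**Step 2: joint power for a given per-test power.** Take both test statistics as normal with unit variance. For 80% power at one-sided 0.025, each has mean 1.96 + 0.84 = 2.80. Joint power is the bivariate normal probability that both exceed 1.96. At r = 0 this is 0.80 × 0.80 = 0.64.

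| Per-test power | r = 0 | r = 0.3 | r = 0.5 | r = 0.7 | r = 0.9 |
|---|---|---|---|---|---|
| 80% | 64.0% | 66.6% | 68.7% | 71.3% | 75.0% |
| 85% | 72.2% | 74.2% | 75.8% | 77.8% | 80.8% |
| 90% | 81.0% | 82.2% | 83.2% | 84.7% | 86.9% |

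In the first row the result stays below 80% for any r under 1.

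**Step 3: per-test power needed for joint 80%.** Solving the same probability for 0.80 gives 89.4% per test at r = 0 (√0.80 = 0.894) and 87.9% at r = 0.5. For one dose against placebo with N = 36, 89.4% needs ρ of about 0.85; for pooled doses, about 0.80.

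**Step 4: what the split does to power.** Hold the mean of the test statistic at 2.80. At one-sided 0.05, per-test power is Φ(2.80 − 1.645) = 87.6%; at 0.025 it is 80%. The split lowers per-test power, and joint power with it: from 76.8% to 64.0% at r = 0.

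**The case against.** **Each, not both.** The wording may mean 80% power for each outcome separately. The closing sentence of Section 5.4 is softer and refers to tests in the plural, and a Bonferroni split suits a claim on either outcome. This reading is available, and on it no calculation is shown to be wrong. The text still credits the alpha split with achieving the power, and its capitalised emphasis invites the joint reading, so it needs rewording either way.

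**More than 80%.** The plan says greater than 80% and does not show the calculation. At 90% per test, joint power would be 81% to 87%, so a true joint figure above 80% cannot be excluded. This stands. A reader might infer that the trial's joint power is 64% to 75%, but the documents do not support that as a fact about the trial. It follows only if per-test power is exactly 80%.

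**A step-down test.** With 80% per test at the first step, Holm's procedure would give joint power of 76.2%, 78.7%, 80.2% and 81.9% at r = 0, 0.5, 0.7 and 0.9. It would therefore meet the target at high correlation. The plan specifies Bonferroni and assumes no such correlation.

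**A larger pupil effect.** The pilot estimate was 2.98, but Section 5.4 declines to rely on it and powers both outcomes at 0.3. The claim has to be judged at 0.3.

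**Consequences for the trial's conclusions.** A reader might infer that the trial succeeds only if both outcomes are significant, or that a split result would count as evidence against the other outcome. The protocol says neither. It ranks pupil diameter as the primary hypothesis and CAPS-5 as the secondary one, and joint detection appears only in the sample-size argument.

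**Conclusion.** The point holds as a claim not supported by the step offered for it. The alpha split cannot deliver joint power, and the stated inputs can at most define a power for each outcome. The size depends on the unshown per-test power. At exactly 80% per test, joint power is 64% to 75% over correlations 0 to 0.9, a shortfall of 16 to 5 percentage points against the stated 80%.

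These figures assume equal effects of 0.3, normal test statistics and 36 subjects completing all periods. The unstated within-subject correlation is a separate gap beneath this one, since 80% per test itself depends on it. Supplying a value that gives 80% per test would still leave the joint claim unsupported.

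**What to change.** Keep N = 36 and revise Section 5.4 as follows.

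1. Delete the statement that Bonferroni correction achieves 80% power for both outcomes. Describe the split only as control of false positives across two tests.
2. State the power for each outcome at one-sided 0.025, together with the contrast and the within-subject correlation it assumes. A figure of 80% needs about 0.80 for one dose against placebo, or about 0.73 for pooled doses against placebo. It should not be restated without that assumption.
3. State the resulting joint power over a range of cross-outcome correlations, for example 64% to 75% at correlations 0 to 0.9 if per-test power is 80%.

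The cost is some rewording and a short calculation, with no change to sample size or conduct. The downside is that a stated figure becomes less favourable.

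### Section 5.4: replacing plain Bonferroni with Holm would raise the chance of detecting both effects at the same one-sided familywise 0.05

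*Combined protocol and SAP*

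**What the plan says.** Section 5.4 gives the reason for the adjustment: "In order to address the issue of powering for 2 outcome measures we will employ Bonferoni correction to be conservative". It adds that "Bonferoni correction for 2 tests dictates that we divide" 0.05 by two, and it places the 0.025 "level in a one-tailed test of significance". The goal is joint: with 36 subjects the plan expects to "achieve greater than 80% power to detect effects with BOTH the CAPS-5 and pupil measure". On the inputs it says: "This calculation assumed an effect size of 0.3 for both the CAPS-5 score and for the pupil measure". Effect size is defined there as Cohen's d on the overall standard deviation.

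The closing sentence of 5.4 explains the adjusted level as one "for detecting effects on 2 primary outcomes at the 0.05 level". The hypotheses listed at the end of section 5.3 rank the outcomes differently. Pupil diameter is the primary hypothesis, and the next entry reads "Secondary Hypothesis: Brexpiprazole therapy will be associated with a dose-dependent decrease in CAPS-5 scores".

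Section 3 lists three aims under Primary Objectives. PTSD severity is the second, and the third begins "Specific Aim 3: 1) Evaluate whether depression severity improves with treatment". No section mentions a step-down procedure or a fixed testing order.

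**The concern.** Plain Bonferroni holds both outcomes to 0.025 whatever the other one shows. Once one outcome has passed 0.025, only one hypothesis is left to protect, and it can be tested at the full 0.05 without raising the familywise error. Holm uses this and Bonferroni does not. The unused allowance matters little for finding at least one effect, because the first step of the two rules is identical. It matters for finding both, which is what section 5.4 says it wants. In a 36-subject pilot, the result most exposed is one where one outcome is clearly significant and the other has a one-sided p between 0.025 and 0.05.

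The CAPS-5 label matters here because it decides which procedure fits. Two co-primary outcomes suit Holm, and a ranked primary and secondary suit a fixed sequence.

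**Working it through.** **Inputs from section 5.4.** n = 36; overall one-sided level 0.05; two outcomes; effect 0.3 for each, standardised by the overall SD; goal above 80% for both.

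**Assumptions, not in the plan.** One contrast per outcome, analysed as a paired t test with 35 df; equal effects on both outcomes; no dropout; a within-subject correlation rho; and a correlation c between the two outcomes.

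**The plan's own figures.** The split reproduces: 0.05/2 = 0.025. With independent tests the familywise error is 1 − 0.975² = 0.0494.

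The power above 80% cannot be reproduced, because no rho, contrast or test is stated. The paired effect is dz = 0.3/√(2(1 − rho)).
- At rho = 0.5, dz = 0.3 and power per outcome at 0.025 is 42%.
- 80% per outcome needs dz = 0.48, that is rho of about 0.805: 0.3/√(2 × 0.195) = 0.48.
- 80% for both, if independent, needs √0.80 = 89.4% each. That is dz = 0.55, or rho of about 0.851: 0.3/√(2 × 0.149) = 0.55.

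These three values of dz therefore cover the readings in which the claim fails, holds per outcome, and holds jointly.

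**Rules.** Bonferroni finds both if both p ≤ 0.025. Holm finds both if the smaller p ≤ 0.025 and the larger p ≤ 0.05. Any pair that meets the first condition meets the second.

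**Familywise error under Holm.** If both nulls are true, any false rejection requires the smaller p ≤ 0.025, as under Bonferroni, so the error is at most 0.05. If one null is true, a false rejection requires that outcome's p ≤ 0.05, so the error is again at most 0.05.

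**Joint power, independent outcomes.** Let p1 and p2 be the power of one test at 0.025 and 0.05 (noncentral t, noncentrality dz × √36 = 6dz). Both significant: Bonferroni p1²; Holm 2·p1·p2 − p1².

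| dz | p1 | p2 | Bonferroni | Holm | Gain (points) |
|---|---|---|---|---|---|
| 0.30 | 0.4171 | 0.5478 | 0.174 | 0.283 | 11 |
| 0.48 | 0.7996 | 0.8808 | 0.639 | 0.769 | 13 |
| 0.55 | 0.8940 | 0.9441 | 0.799 | 0.889 | 9 |

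First row in full: 0.4171² = 0.174; 2 × 0.4171 × 0.5478 − 0.174 = 0.457 − 0.174 = 0.283.

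**Correlated outcomes.** Simulating 400,000 trials per setting at c = 0.8, both-significant rises from 31.3% to 41.6% (dz 0.30), 72.7% to 81.3% (0.48) and 84.8% to 90.7% (0.55). The gains are about 10, 9 and 6 points.

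**Fixed sequence, for comparison.** Both significant requires both p ≤ 0.05, so at independence the probability is p2²: 0.300, 0.776 and 0.891. This is slightly above Holm, but CAPS-5 cannot be claimed if pupil diameter fails.

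**The case against.** The case for leaving 5.4 alone is a fair one.

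- **Bonferroni is valid, disclosed and chosen for caution.** This stands. It controls error whether CAPS-5 is co-primary or secondary. A reader might infer that the alpha rule is wrong; the documents do not support that.
- **The plan already claims more than 80% for both.** Taken literally as joint power, the goal is met under Bonferroni, and Holm only moves about 80% to 89%. That stands as a reading. The claim cannot be checked from the stated inputs, though, and Holm gains under every reading.
- **The 17% to 28% figures treat 0.3 as a paired effect, whereas the plan standardises by the overall SD.** Correct. That row corresponds to rho = 0.5 and is only one of three cases.
- **Holm lets the second outcome be declared at one-sided 0.05 in tests that are already one-tailed.** True, and it is the real price. If only one effect exists, the other outcome can be falsely declared with probability up to 0.05 instead of 0.025. That is still within the overall level the plan set for itself. A sponsor may prefer the stricter threshold, but should say so.
- **Holm does not secure 80%.** Also true: at dz = 0.48 with independent outcomes it reaches 77%. The missing within-subject correlation affects power more than the choice of procedure does.

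Two further inferences are tempting. A reader might conclude that sections 3, 5.3 and 5.4 define three competing confirmatory families. Only 5.4 sets an alpha; section 3 lists aims without tests, and the depression, nightmare and sleep items of Aim 3 have no hypothesis in 5.3. A reader might also say that a CAPS-5 result at p = 0.04 could be called a success or a failure depending on the section read. No section gives CAPS-5 any threshold other than 0.025, so under the written rule it is not significant.

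**Conclusion.** The point holds as an efficiency improvement and not as an error in the plan. Holm never loses a rejection that Bonferroni makes and keeps the one-sided familywise level at 0.05. For the stated aim of detecting both effects, it adds about 9 to 13 percentage points with independent outcomes and about 6 to 10 at an outcome correlation of 0.8. These figures assume 36 subjects with complete data, one contrast per outcome, equal effects and paired effects between 0.30 and 0.55. The dominance of Holm over Bonferroni does not depend on those assumptions; the size of the gain does.

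The difference in the CAPS-5 label between 5.3 and 5.4 is real, but it needs only a consistency edit. Changing the procedure does not establish the power above 80%, which remains unverified until the within-subject correlation is stated.

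**What to change.** In section 5.4, replace Bonferroni with Holm on the two one-sided p-values: compare the smaller with 0.025 and, only if it passes, compare the larger with 0.05.

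Reconcile the status of CAPS-5 between 5.3 and 5.4. If the two outcomes are co-primary, Holm fits as written above. If the sponsor intends the 5.3 ranking, use a fixed sequence: pupil diameter at one-sided 0.05, then CAPS-5 at one-sided 0.05 only if pupil diameter succeeds.

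The cost is a change of wording made before unblinding, with no extra subjects, visits or data. The one consequence is that the second outcome may be declared at one-sided 0.05, the plan's own overall level. Holm on two p-values needs one pre-specified contrast per outcome. The present count of two tests already implies this, but with two active doses and placebo (section 5.2) that contrast still has to be named.
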